STATISTICAL ANALYSIS PLAN

Depression Return to Work Intervention (DRIVEN)

Version 1.0

Sites: Inspiration at Work, Northwestern University, University of Chicago

Version 1.0 Date: 17 July 2024

Principal Investigators: [name], [name], &
[name]

NCT#: NCT06026280

Introduction

Study Background

Unemployment can be a time of high emotional distress; in turn, this emotional distress can interfere with active behaviors needed for finding a job, such as preparing for interviews, networking, revising one's résumé, and researching employment opportunities. Occupational impairment can be part of having a mental disorder (e.g., being unable to work due to major depressive disorder). Thus, interventions are needed that support job seekers during unemployment, which is often associated with high distress.

Study Objectives

The goal of this study is to use a randomized controlled trial (RCT) design to evaluate a six-week intervention (DRIVEN) that provides both job coaching, cognitive-behavior activities, and a mobile app that are intended to help participants cope with unemployment-related distress. The comparison condition is self-guided job seeking in which the participant receives standard job search recommendations by email each week.

The **primary outcome measures are the two subscales of the Job Search Behavior questionnaire – preparatory job search behavior and active job search behavior.** Secondary outcomes include employment status (i.e., whether the person found a job) and symptoms of depression. We will also test the hypothesis that a bidirectional relationship exists between job search behavior and depression using a cross-lagged panel model.

Statistical methodology

Overview

Data will be summarized by group and in total. In summary tables of continuous variables, we will report the range, mean, and standard deviation. We will also inspect the median and semi-interquartile range and report as needed. We will use counts and percentages in tables for categorical variables. The denominator for each percentage will be the number of participants within the group unless otherwise specified. Hypothesis testing will be carried out at a two-tailed Type I error rate of $\alpha = .05$ (e.g., for comparing full to reduced regression models), and/or corresponding 95% confidence intervals (e.g., for interpretation of regression coefficients) unless otherwise specified. If statistical methods change during analysis (e.g., non-normality of residuals, heteroscedasticity), the changes will be documented in the write-up of the results along with justification. Additional analyses of these data will be inevitable, but any exploratory analyses will be clearly marked as such.

Statistical power analysis and sample size selection

In planning the DRIVEN trial, various scenarios around different effect sizes, sample sizes, drop-out rates, and variance estimates were considered. For the possibility of finding a job as an outcome, we used *powerSurvEpi* in R^{1,2} to estimate power for proportional hazard models under different conditions of sample size, hazard ratios, and probability of job-finding. With a 10% difference between groups (e.g., 35% vs 45% chance of finding a job) power is 80% with the proposed $N = 50$ per group (total $N = 100$, although 126 will be recruited to account for 20% up to attrition). Effects smaller than 10% would not be clinically/practically meaningful, and we would be underpowered for these smaller effect sizes. For continuous outcomes, we conducted Monte Carlo simulations following guidance from the clinical trial literature and we included longitudinal assessments each week to achieve a "longer", and thus more powerful, data set. We assumed a Type I error rate of .05 and based effect-size and variance estimates on previous research.^{2,3} Simulations indicated that power for the time \times DRIVEN interaction would be 94% even for medium-sized effects (treatment effect = 0.7), and assuming a drop-out rate of 20%. We examined power for a variety of simulated conditions (e.g., sample size, effect size), which led us to

an overall sample size of $N = 126$ overall. Power for simple between-group comparisons of continuous outcomes (e.g., job search behavior) was also examined in the *pwr* package of R; these analyses showed 98% power for the DRIVEN vs. self-guided job-seeking group comparison with large effects ($d = 0.8$), and 93% power for smaller effects ($d = 0.7$).

We also planned some auto-regressive analyses, which we anticipate will have high power owing to the large number of repeated measures in the design; power was approximated by considering the number of t and $t + 1$ observations available for associations. Considering all data points (~100 participants times 22 weeks with a prior week available as a predictor), effect sizes as small as $r = .1$ would be detectable (calculations done in *pwr* package), even when missing data were estimated as much as 50% (i.e., half of weeks left incomplete).

We acknowledge that some changes were made to our design after the power analyses were completed (e.g., there are 6 weeks of survey outcomes plus 2 follow ups), but we deemed these changes necessary on practical grounds (e.g., to reduce participant burden) and did not recalculate power. These changes should not imperil statistical power because we have refined our approach to use a simpler model with fewer parameters (i.e., polynomial regression of continuous time, and time \times treatment interaction).

Missing data and outliers

We will approach the analyses from an intent-to-treat perspective. All participants will be included in the mixed modelling, which can be accommodated using the *nlme* package of R. Although we will inspect the data for outliers and influence, we do not plan to drop cases.

Study Timepoints

There is a baseline assessment, six weeks of intervention with weekly surveys, and two follow-up assessments. The baseline assessment will be included as a covariate and not included as part of the outcome. Time will be treated as a continuous variable calculated as “days since baseline”. The mixed effects modelling will include all observations of the Job Search Behavior questionnaire starting from baseline out to the 16-week post-intervention assessment.

The purpose of the two follow-up assessments (8 and 16 weeks) is to (a) provide a period of time for the person to possibly find a job and (b) examine the trajectory of change in the two groups in job search behavior, from during the acute intervention into a 16-week follow-up period.

Interim analyses to ensure data quality

In order to ensure data integrity and quality, we will conduct limited interim data analyses. The goal of this analysis will be to conduct a “dry run” of data management procedures. We will import these data from REDCap and inspect them for data quality, and to test scoring algorithms for questionnaires. In these interim analyses, some preliminary results may be shared with potential investors and/or sponsors of the DRIVEN program, but these analyses will not be submitted for publication. The definitive analyses of the RCT will be as described below.

Primary analyses

Job Search Behavior: Preparatory and Active Job Searching

Because the surveillance period of this study may be too short to evaluate whether the participants found jobs

or not, the primary outcome measure will be the Job Search Behavior questionnaire, which has two separate subscales for preparatory versus active job searching. We will use a mixed model with random intercepts for each participant, using the maximum likelihood estimator. Time will be included as a continuous variable as described above (i.e., days since baseline). Because baseline is included as a covariate and not part of the outcome, we will include both a main effect of treatment as well as interaction effects with time. We will then fit a corresponding model with no effects of treatment. Treatment will be coded as Control = 0; DRIVEN = 1. In this way, the effect of treatment can be evaluated by comparing the full to the reduced model. In R pseudocode, the model will appear as follows:

```

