# Note: Using this R syntax, main effects are also included
# (i.e., tx, t, and t2).
full_model <- lme(jsb ~ tx * t + tx * t2, random = ~1 | id, data = data)
reduced_model <- lme(jsb ~ t + t2, random = ~1 | id, data = data)
```

Alternative approaches and model modifications

Although we hypothesize the models above, it is possible that data-driven modifications will be needed to the model. These include:

- Consideration of an alternative estimator (e.g., REML) and/or bootstrapped confidence intervals
- The possibility the model could be substantially improved by including cubic, etc., effects
- The possibility of random slopes in addition to random intercepts

We have chosen to focus on a simpler model to ease interpretation and to avoid overfitting, but we will adjust the model as needed based on inspection of the results and diagnostics (e.g., inspection of residuals for normality, heteroscedasticity, influential observations).

Mediation analyses to evaluate mechanism

We envision that participants' job seeking will improve as their emotional distress improves, and vice versa. In other words, we hypothesize a bidirectional relationship between job seeking and depression. We will evaluate this using a random-intercept cross-lagged panel⁴ model in *lavaan* in R, using the `missing = "ML"` argument for missing data that allows for ML estimates for missing-at-random data. Each time point will be regressed on the previous time point. Slopes that are equally spaced in time will be constrained to be equal as a means to lower the number of parameters estimated. Because the purpose of this analysis is to evaluate the mechanism of DRIVEN, we will only conduct it in the DRIVEN group. The main outcomes of this analysis will be the magnitude of the cross-lagged regressions – job searching predicting depression, and depression predicting job searching.

Secondary analyses

Analyses of secondary continuous outcomes, and other exploratory analyses, will be done using mixed models, using the same approach as described above.

Because an important secondary outcome is whether the person obtained a job or not, we will also time-to-event analyses (a.k.a., survival analyses) to create hazard curves of "time unemployed". The primary variable of interest will be treatment group, but other exploratory covariates may be added to the model (e.g., do people with higher baseline depression spend more time in unemployment?).

REFERENCES CITED

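### The stated 80% power for job finding (35% vs 45%, 50 per group) is wrong; the plan's own inputs give about 18%

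*SAP*

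**What the plan says.** The section on statistical power and sample size selection describes using an R package "to estimate power for proportional hazard models under different conditions of sample size, hazard ratios, and probability of job-finding". The result reported is: "With a 10% difference between groups (e.g., 35% vs 45% chance of finding a job) power is 80" per cent, with 50 per group. The total of 100 is then raised: "although 126 will be recruited to account for 20% up to attrition". The next sentence reads: "Effects smaller than 10% would not be clinically/practically meaningful, and we would be underpowered for these smaller effect sizes".

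The Overview sets testing at two-tailed 5%. Neither the hazard ratio entered nor the expected number of events is given. Under Secondary analyses, obtaining a job is described as an important secondary outcome, to be analysed by time-to-event methods with treatment group as the main variable.

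**The concern.** A 10-point difference in the middle of the probability scale is a modest effect, and 50 per group is a small sample. In a time-to-event comparison the power comes from the events, and here fewer than half of the participants are expected to have one. A claim of 80% power under those conditions looks far too high.

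What is at stake is how the employment result will be read. The two sentences together tell the reader that the trial is adequately powered at the smallest effect worth having and weak only below it. If that is untrue, a non-significant hazard ratio would be taken as evidence against a worthwhile benefit when it says very little either way.

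**Working it through.** **Inputs, all from the SAP.** Probability of finding a job 35% vs 45%; 50 per group; proportional hazards (power section). Two-sided α = 0.05 (Overview). The hazard ratio and event count are not stated and are derived here, assuming the same follow-up in both groups.

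**Step 1. Hazard ratio.** Under proportional hazards, HR = ln(1 − 0.45)/ln(1 − 0.35) = ln(0.55)/ln(0.65) = 1.388, and ln(HR) = 0.3277.

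**Step 2. Events.** 50 × 0.35 + 50 × 0.45 = 40.

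**Step 3. Trying to reproduce 80%.**
- Schoenfeld: Φ(√(40/4) × 0.3277 − 1.96) = Φ(1.036 − 1.960) = Φ(−0.924) = 17.8%.
- Freedman: Φ(√40 × 0.388/2.388 − 1.96) = 17.5%.
- Comparison of two proportions at 50 per group: 17.3%.
- Simulated log-rank test (20,000 runs, exponential times, 35% and 45% cumulative incidence): 17.3%.

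The four methods agree, and the stated figure is not reproduced.

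**Step 4. Could another reading give 80%?** Schoenfeld formula throughout:

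| Reading | Power |
|---|---|
| 63 per group, no attrition (50.4 events) | 21.3% |
| One-sided 5% | 27.1% |
| Ratio of proportions (1.286) used as the HR | 12.2% |
| Odds ratio (1.519) used as the HR | 26.2% |
| All 100 participants counted as events, HR 1.388 | 37.4% |
| Odds ratio as HR, all 100 as events, one-sided | 67.3% |
| The same three departures with all 126 as events | 75.9% |

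The pair is given only as an example, so other 10-point pairs were tried at 50 per group, two-sided: 5% vs 15% gives 44.6%, 10% vs 20% gives 30.6%, 20% vs 30% gives 21.6%, 40% vs 50% gives 17.5%, 60% vs 70% gives 19.5% and 80% vs 90% gives 37.9%. Only pairs at the very edge of the scale reach 80% (1% vs 11%: 85.1%; 89% vs 99%: 94.6%).

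**Step 5. What 80% would need.**
- Events: 4 × (1.960 + 0.842)² / 0.3277² ≈ 292.4, so 293 (Freedman: 298).
- Participants: 293/0.40 = 732.5, so about 733; with 20% attrition, 733/0.8, so about 917.

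**Step 6. What 50 per group can detect.** With 35% in control, Schoenfeld power is 77.3% at 61% in the other arm and 80.4% at 62%, where HR = ln(0.38)/ln(0.65) = 2.25. The two-proportion comparison first passes 80% at 63% (80.9%). The Freedman form does so at 64%: HR 2.37, 49.5 events, Φ(√49.5 × 1.37/3.37 − 1.96) ≈ 82%. The detectable difference is therefore about 27 to 29 points.

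**Step 7. Attrition.** 100/0.8 = 125, so recruiting 126 fits a 20% loss. That step is not the source of the error.

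**The case against.** The strongest reply is that job finding does not carry the trial. Job Search Behavior is primary, and the Primary analyses section says so because follow-up may be too short to judge employment. The power section ties the total of 126 to simulations for the continuous outcomes. All of that is right: the error does not by itself undermine the sample size for the primary outcomes. It does not withdraw the 80% claim, however, and a follow-up too short to see jobs found would mean fewer events and still less power.

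A second reply is that the hazard ratio used was never disclosed. With 40 events, an HR of exp(2 × 2.802/√40) = 2.43 would return 80%, so a mismatched input may be the cause. The document cannot settle this. Such a ratio would turn 35% into 1 − 0.65^2.43 ≈ 65%, not 45%, so the sentence would still be wrong.

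Third, the SAP concedes that design changes followed the power work and that power was not recalculated. The mismatch lies within the stated inputs, so later changes do not explain it.

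Fourth, the sentence about smaller effects is literally true: power is low below 10 points. It misleads only beside the 80% claim, by implying that power is adequate at 10 points. It is not a separate arithmetic error. Nor does the SAP say how a non-significant employment result will be interpreted; the risk comes from how readers would use the stated power.

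**Conclusion.** The concern holds. At 35% vs 45% with 50 per group and two-sided 5% testing, power is 17% to 18%, not 80%; with all 126 retained it is about 21%. The stated figure is more than four times too high, and the trial would miss the difference that the SAP treats as the smallest worthwhile one about four times in five. The comparison can still be run and reported, but it is severely underpowered at that effect.

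The result assumes proportional hazards, equal follow-up in the two groups and 1:1 allocation. It does not depend on the choice of formula, and no plausible reading of the stated pair approaches 80%.

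**What to change.** Keep the sample size. Replace the power statement with wording such as: *With 50 per group, power to detect 35% vs 45% finding a job is about 18%; the smallest difference detectable with 80% power is about 35% vs 62% (hazard ratio about 2.25).* Name the formula used, since other methods put the second figure at 63% to 64%, and state the hazard ratio and expected events.

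Revise the following sentence so that it no longer implies adequate power at 10 points. Under Secondary analyses, say that the employment comparison will be reported as a hazard ratio with its 95% confidence interval, which the Overview already allows for, and that a non-significant result is not evidence that a worthwhile effect is absent.

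The cost is SAP wording only. No endpoint, procedure or analysis changes; the stated power simply becomes less favourable.

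### The 94% power for the time × DRIVEN interaction belongs to a superseded visit schedule and a different test, and the assurance that power is safe is unsupported

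*SAP*

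**What the plan says.** All power statements are in the SAP section Statistical power analysis and sample size selection.

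- Monte Carlo simulation was used for continuous outcomes. Weekly assessment was included expressly because a longer series gives more power. Power for the time × DRIVEN interaction "would be 94% even for medium-sized effects (treatment effect = 0.7), and assuming a drop-out rate of 20" percent.
- For the auto-regressive analyses, the observations are counted as "100 participants times 22 weeks with a prior week available as a predictor". Twenty-two weeks equals 6 intervention weeks plus 16 follow-up weeks.
- The section then discloses that the design changed after these calculations, so that now "there are 6 weeks of survey outcomes plus 2 follow ups", and that power was not computed again. It adds: "These changes should not imperil statistical power because we have refined our approach to use a simpler model with fewer parameters".

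Under Primary analyses, the model has random intercepts, linear and quadratic time, and maximum likelihood estimation, and "the effect of treatment can be evaluated by comparing the full to the reduced model". In the pseudocode the two models differ by tx, tx:t and tx:t2.

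**The concern.** The SAP gives a power for its primary outcome that was not computed for the visits it now plans or for the test it now plans.

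The assurance does not fill the gap. Precision of a time-by-treatment effect depends on how many visits there are, how they are spread and how they are correlated. Dropping fixed-effect parameters does not bring back lost visits. The same section credits the weekly visits with the power, so it cannot also treat their removal as harmless without a calculation.

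At stake is how a null result would be read. A reader who takes 94% at face value would see a null result as strong evidence against an effect of the stated size, when the figure does not belong to this design. The simulations are also among the reasons given for N = 126.

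**Working it through.** **Inputs**

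- Type I error: "We assumed a Type I error rate of .05". The test is two-sided (SAP, Overview: "Hypothesis testing will be carried out at a two-tailed Type I error rate of" .05).
- Sample size: 50 per group after attrition, "although 126 will be recruited to account for 20% up to attrition". Check: 126 × 0.80 = 100.8, about 50 per group.
- Stated interaction power: 94%.
- Earlier schedule: weekly, weeks 1 to 22. *Assumption*: the SAP gives 22 weeks for the auto-regressive calculation, not explicitly for this simulation.
- Current schedule: weeks 1 to 6, 14 and 22. *Assumption*: the follow-ups at 8 and 16 weeks are counted from the end of the intervention, as Study Timepoints suggests when it calls the last one post-intervention.

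**1. The SAP's own figures.** The 94% cannot be reproduced, because no variance components, within-person correlation, effect unit or analysis model are given for it. The simple two-group figures do reproduce. For a two-sample t-test with 50 per group, the non-centrality is d × √(50/2) = 5d on 98 df. At d = 0.8 (5d = 4.0) power is 97.7%, against the stated 98%. At d = 0.7 (5d = 3.5) it is 93.4%, against the stated 93%. These figures do not depend on the visit schedule.

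**2. Slope information, illustrative.** With random intercepts and independent residuals, information on a linear slope is proportional to Sxx = Σ(t − mean t)².

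- Weeks 1 to 22: mean 11.5, Sxx = 885.5
- Weeks 1 to 6, 14, 22: mean 7.125, Sxx = 364.9
- Ratio: 364.9 / 885.5 = 0.412

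**3. Rescaled power, 1-df slope test.** Power of 94% needs a non-centrality of 1.960 + 1.555 = 3.515. On the current visits this becomes 3.515 × √0.412 = 2.256, so power = Φ(2.256 − 1.960) = 61.6%.

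**4. How far this depends on assumptions**

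*Random slopes.* Let r be the slope variance in units of the 22-week sampling variance of one person's slope. The information ratio is (r + 1)/(r + 2.427), where 2.427 = 885.5/364.9.

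| r | ratio | power |
|---|---|---|
| 0.5 | 0.51 | 71% |
| 1 | 0.58 | 77% |
| 2 | 0.68 | 82% |
| 4 | 0.78 | 87% |
| 10 | 0.89 | 91% |
| 20 | 0.94 | 93% |

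*Serial correlation.* With AR(1) residuals, week-to-week correlation ρ and no random slope:

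| ρ | ratio | power |
|---|---|---|
| 0.3 | 0.60 | 78% |
| 0.5 | 0.75 | 86% |
| 0.7 | 0.90 | 92% |
| 0.9 | 0.996 | 94% |

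*Timing.* If 8 and 16 weeks ran from baseline, Sxx = 157.9, the ratio is 0.18 and step 3 gives 32%.

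**5. The planned test.** Full versus reduced tests tx, tx:t and tx:t2 together on 3 df. Its non-centrality is (50/2) × b′(X′V⁻¹X)b, with X = (1, t, t²), V the random-intercept covariance and b the three treatment coefficients. Two calibrations give opposite pictures.

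- *Tied to the 94%.* The effect grows linearly from zero at baseline and is scaled so that the 1-df slope test has 94% power on 22 weekly visits. The 3-df power on the current visits is then 55%, 50% and 47% at within-person correlation 0.3, 0.5 and 0.7.
- *Tied to 0.7, read as 0.7 total SD.* On the current visits, over the same correlations, power is 94% to 99.9% for a constant effect, 99.5% or more for an effect that rises to week 6 and then stays level, and 94% to 99.9% for a linear rise to week 22. At 0.5 total SD the range over these shapes is 68% to 95%.

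The second reading does not explain the 94% for a linear rise to week 22: the 1-df slope test on 22 weekly visits would then have power near 100%.

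**The case against.** The strongest reply is that the assurance may turn out to be true. The primary test includes the main effect of treatment, which loses little when visits are cut, and step 5 shows 94% or more on the current visits if 0.7 means 0.7 total SD. Weekly self-reports of behaviour are probably serially correlated, and then the dropped visits carried less new information. The model was changed too, and the earlier one is not described, so the rescaling has no established starting point. N = 126 does not rest on this figure alone: the section ties 50 per group to the job-finding outcome as well, and the two-group power is unaffected. The SAP also discloses the change openly.

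All of this stands as a limit on the size of the loss. A reader might infer that power on the current design is 62%, or that the assurance is false and the trial underpowered. The documents support neither. The 62% needs 22 simulated weekly surveys, follow-ups at weeks 14 and 22, a purely linear effect, independent residuals, no slope variance and a 1-df test.

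The reply does not supply a power for the planned design, and it does not rescue the argument from fewer parameters. Disclosing that a figure is out of date does not make it apply.

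**Conclusion.** The point holds in this form: the 94% was computed for a superseded schedule and for an interaction rather than the planned 3-df comparison, and the assurance that power is not endangered is unsupported.

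Power on the current design is unknown. Taking the stated 94% as the starting point, a 1-df slope test would have about 62% under random intercepts with independent residuals, about 71% to 93% over most of the random-slope and serial-correlation settings tried, and essentially the same 94% at serial correlation 0.9. These figures assume 22 weekly surveys in the simulation and follow-ups at weeks 14 and 22. Power for the 3-df test could still be 94% or more if 0.7 is in total SD units. The inputs that would settle the matter are not stated.

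**What to change.** In Statistical power analysis and sample size selection:

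1. Delete the sentence claiming that the changes should not endanger power.
2. Rerun the existing simulation on the current visits (six weekly surveys and two follow-ups, with their timing stated in weeks from baseline), with 20% drop-out, for the planned 3-df likelihood-ratio test of full against reduced model.
3. State the unit of the treatment effect of 0.7, the assumed shape of the effect over time, the variance components and the within-person correlation.
4. Replace 94% with the resulting figure, and say that it was computed after the schedule change and without changing N.

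The cost is one rerun of existing code and a few lines of text, with no extra participants. The downside is that the stated power may become less favourable.

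### The claim that r = .1 is detectable with half the weeks missing rests on about 2,200 lagged pairs; the planned DRIVEN-only weekly slope has 300 to 378

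*SAP*

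**What the plan says.** In the SAP section on statistical power analysis and sample size selection, power for the auto-regressive analyses is approximated by treating the number of week-to-week pairs as the sample size of a simple correlation. The count is given as "Considering all data points (~100 participants times 22 weeks with a prior week available as a predictor". The text concludes that r = .1 is detectable, "even when missing data were estimated as much as 50% (i.e., half of weeks left incomplete". The same section plans for 50 per group, 100 in total, "although 126 will be recruited to account for 20% up to attrition". So the 100 participants are both arms together.

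The next paragraph says the design changed after the power work was done ("there are 6 weeks of survey outcomes plus 2 follow ups") and that power was not recalculated. It adds: "These changes should not imperil statistical power because we have refined our approach to use a simpler model with fewer parameters". The simpler model it names is the polynomial regression on time with a time-by-treatment interaction.

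Study Timepoints confirms the schedule: "There is a baseline assessment, six weeks of intervention with weekly surveys, and two follow-up assessments".

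Under Mediation analyses to evaluate mechanism, the lagged model is a random-intercept cross-lagged panel model in which only slopes over equal time spacing are constrained to be equal. Its population is restricted: "Because the purpose of this analysis is to evaluate the mechanism of DRIVEN, we will only conduct it in the DRIVEN group".

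**The concern.** The power statement and the analysis it supports differ in two ways. The schedule was cut from 22 lagged weeks to at most eight lags per person, and the lagged model uses one arm instead of two. The equal-spacing rule then separates the weekly slope from the follow-up slopes, so the weekly slope draws on only six of the eight lags.

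The SAP bases its expectation of high power for these analyses on the large number of repeated measures, which is the quantity that was reduced. The reassurance that follows argues from a different model, and the power text does not mention the one-arm restriction.

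The bidirectional link between job search and depression is a stated study objective, and the cross-lagged coefficients are the main outputs of the mechanism analysis. If r = .1 is declared detectable, a non-significant cross-lag could be read as evidence against the mechanism when the analysis had less than an even chance of finding it.

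**Working it through.** **Inputs from the SAP.** Two-sided alpha .05; r = .1; pairs treated as independent; 50 per group after attrition; 126 recruited; baseline, six weekly surveys and two follow-ups; lagged model in DRIVEN only; slopes equal only over equal spacing.

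**Assumptions.** Allocation is 1:1, so 126/2 = 63 in DRIVEN. Baseline to week 1 counts as a weekly lag. The auto-regressive analyses of the power section are the cross-lagged model, the only lagged model specified. The 80% benchmark is ours, because the SAP attaches no power level to the word detectable.

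**Formula.** Fisher z: power = Phi(atanh(r) x sqrt(n - 3) - 1.96), with atanh(.1) = 0.1003. The formula in the *pwr* package, which the SAP used, agrees to within about 0.2 percentage points.

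**The SAP's own figure.**
- 100 x 22 = 2,200 pairs: 0.1003 x sqrt(2,197) - 1.96 = 2.74, power 99.7%.
- 50% missing, 1,100 pairs: 0.1003 x sqrt(1,097) - 1.96 = 1.36, power 91%.

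So the claim reproduces on its stated inputs.

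**The current plan, DRIVEN weekly slope.**
- 50 x 6 = 300 pairs: 0.1003 x sqrt(297) - 1.96 = -0.23, power 41%.
- 63 x 6 = 378 pairs: 0.1003 x sqrt(375) - 1.96 = -0.02, power 49%.
- Halved, 150 and 189 pairs: 23% and 28%.

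**Pairs needed.** ((1.96 + 0.84)/0.1003)^2 + 3, about 782 for 80% power at r = .1.

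**Detectable r at 80% power.** About 0.16 (300 pairs) and 0.14 (378); about 0.23 (150) and 0.20 (189).

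**Other readings at r = .1:**

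| Reading | Pairs | Power |
|---|---|---|
| DRIVEN, baseline lag not counted (5 lags) | 250-315 | 35-43% |
| DRIVEN, follow-up slope, if both gaps are 8 weeks (2 lags) | 100-126 | 17-20% |
| DRIVEN, all 8 lags sharing one slope | 400-504 | 52-61% |
| The same, 50% missing | 200-252 | 29-35% |
| Both arms, 6 weekly lags (N = 100 or 126) | 600-756 | 69-79% |
| Both arms, 8 lags, N = 100 | 800 | 81% |
| The same, 50% missing | 400 | 52% |
| Both arms, 8 lags, N = 126, 50% missing | 504 | 61% |

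No DRIVEN-only reading reaches 80%. With both arms and all eight lags, complete data would just support r = .1, but the 50%-missing clause fails on the schedule change alone.

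**Is the pair count too pessimistic?** The pair count is not the power of the random-intercept model, so large-sample Wald power was also computed for that model. It had nine waves, equal weekly slopes over six lags and separate equal slopes over two follow-up lags. The following values are assumed and are not in the SAP: standardised cross-lags of 0.1 in both directions, weekly stability 0.1 to 0.5, between-person share of variance 0.3 to 0.7, within-wave correlation 0 to -0.4, intercept correlation -0.3 and follow-up stability 0.1. Power for the weekly cross-lag was 30-39% with 50 people and 36-48% with 63. With half the post-baseline waves missing completely at random it was 11-19% and 13-23%. In this range the pair count is not pessimistic.

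**The case against.** The strongest reply is that nothing was miscalculated. The arithmetic is right for its inputs, and the SAP openly says that the schedule changed and power was not redone. This is true, and the fault is one of superseded inputs. But the disclosure is followed by an assurance drawn from the mixed model, which has no bearing on the cross-lagged slopes, and the restriction to one arm is not carried into the power text.

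Second, the replacement figures rest on readings. Baseline may not be a wave in the cross-lagged model, which gives 35-43%. Halving the pairs is only one way to represent half the weeks missing. A pair needs both weeks, so with independent missingness about a quarter would be complete: 300/4 = 75 to 378/4, about 95 pairs, or 14-16% power. Both alternatives enlarge the shortfall. In the other direction, maximum likelihood may recover some information from partial records.

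Third, the consequence is limited. N = 126 does not rest on this sentence, and the planned 95% intervals will show the imprecision: about 1.96/sqrt(375) = 0.10 to 1.96/sqrt(297) = 0.11 either side on the z scale with complete data. This stands, and it keeps the point modest. It does not make the power statement correct.

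Fourth, writing pair-count percentages into the SAP could replace one optimistic figure with another. This is fair, and it makes deletion or simulation the better remedy.

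**Conclusion.** The concern holds. The SAP claims a power property for the lagged analysis that its own approximation does not support under the current plan. The weekly DRIVEN slope has about one-sixth of the stated pairs (378/2,200 = 17% at most). Power at r = .1 is about 41-49% with complete data and 23-28% with half the pairs missing. The lower ends use 50 people, which already allows for attrition; the upper ends use 63 and assume 1:1 allocation. The figures treat pairs as independent, as the SAP does, and are not the power of the random-intercept model. The failure of the 50%-missing clause does not depend on these choices: no reading of the current schedule examined reaches 80% under it, even with both arms and all eight lags. Power for the primary analysis is outside this point.

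**What to change.** Delete the sentence claiming that r = .1 is detectable with 50% missing, or replace it with a simulation of the planned DRIVEN-only random-intercept cross-lagged model under the current schedule, with the assumed parameter values stated.

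If the pair count is kept, restate it with current counts and label it approximate: weekly slope about 41-49% power at r = .1 with complete data and 23-28% with half the pairs missing, and r of about 0.14-0.16 and 0.20-0.23 respectively detectable at 80% power. State whether baseline is a wave of this model.

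Limit the assurance about the design changes to the mixed model.

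The cost is SAP wording or one small simulation, and a less favourable stated power figure. Sample size, data collection and the primary analysis do not change.
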